## **13.4 Termination of the study**

UCB reserves the right to temporarily suspend or prematurely discontinue this study either at a single site, multiple sites, or at all sites at any time for reasons including, but not limited to, safety or ethical issues, inaccurate or incomplete data recording, noncompliance, or unsatisfactory enrollment with respect to quality or quantity.

If the study is prematurely terminated or suspended, UCB (or its representative) will inform the Investigators/institutions and the regulatory authority(ies) of the termination or suspension and the reason(s) for the termination or suspension, in accordance with applicable regulatory requirement(s). The IRB/IEC should also be informed and provided with reason(s) for the termination or suspension by the Sponsor or by the Investigator/institution, as specified by the applicable regulatory requirement(s). In addition, arrangements will be made for the return of all unused IMP and other material in accordance with UCB procedures for the study.

## **13.5 Archiving and data retention**

The Investigator will maintain adequate records for the study, including eCRFs, medical records, laboratory results, Informed Consent documents, drug dispensing and disposition records, safety reports, information regarding participants who discontinued, and other pertinent data.

All essential documents are to be retained by the Investigator until at least 2 years after the last approval of a marketing application in an ICH region and until there are no pending or contemplated marketing applications in an ICH region, or at least 2 years have elapsed since the formal discontinuation of clinical development of the IMP. These documents should be retained for a longer period, however, if required by the applicable regulatory requirement(s) or by an agreement with UCB (CPMP/ICH/135/95, 2002 [Section 4.9.5]). The Investigator will contact UCB for authorization prior to the destruction of any study records or in the event of accidental loss or destruction of any study records. The Investigator will also notify UCB should he/she relocate or move the study-related files to a location other than that specified in the Sponsor's study master file.

### **13.6 Audit and inspection**

The Investigator will permit study-related audits mandated by UCB, after reasonable notice, and inspections by domestic or foreign regulatory authorities.

The main purposes of an audit or inspection are to confirm that the rights and well-being of the subjects enrolled have been protected, that enrolled subjects (ie, signing consent and undergoing study procedures) are appropriate for the study, and that all data relevant for the evaluation of the IMP have been processed and reported in compliance with the planned arrangements, the protocol, investigational site, and IRB/IEC SOPs, ICH GCP, and applicable regulatory requirements.

The Investigator will provide direct access to all study documents, source records, and source data. If an inspection by a regulatory authority is announced, the Investigator will immediately inform UCB (or designee).

### **13.7 Good Clinical Practice**

Noncompliance with the protocol, ICH-GCP, or local regulatory requirements by the Investigator, institution, institution staff, or designees of the Sponsor will lead to prompt action by UCB to secure compliance. Continued noncompliance may result in the termination of the site's involvement in the study.

## **14 STATISTICS**

A description of statistical methods is presented below and will be described in more detail in the statistical analysis plan (SAP).

### **14.1 Definition of analysis sets**

The Enrolled Set (ES) will consist of all subjects who have given informed consent.

The Randomized Set (RS) will consist of all randomized subjects.

The Safety Set (SS) will consist of all subjects who received at least 1 dose of the study medication.

The Full Analysis Set (FAS) will consist of all randomized subjects who received at least 1 dose of the study medication and have a valid measurement of the primary efficacy variable at Baseline.

The Per-Protocol Set (PPS) will consist of all subjects in the FAS who had no important protocol deviation affecting the primary efficacy variable. The subjects with important protocol deviations will be pre-defined and evaluated during a data evaluation meeting prior to unblinding of the data.

The Pharmacokinetics Per-Protocol Set (PK-PPS) will consist of all randomized subjects who took at least 1 dose of the study medication and provided at least 1 quantifiable plasma concentration post-dose.

The Pharmacodynamics Per-Protocol Set (PD-PPS) will consist of all randomized subjects who took at least 1 dose of the study medication and provided at least 1 PD measurement post-dose without important protocol deviations affecting the measurement.

## 14.2 General statistical considerations

Summary statistics will consist of frequency tables for categorical variables. For continuous variables, summary statistics will consist of the number of available observations, arithmetic mean, standard deviation, median, minimum, and maximum unless stated otherwise.

All statistical tests will be performed based on a 2-sided significance level of 5% unless stated otherwise.

## 14.3 Planned efficacy analyses

### 14.3.1 Analysis of the primary efficacy variable

The primary efficacy variable will be analyzed for all subjects in the FAS.

The dose-response relationship between treatment and PASI90 response will be assessed using a logistic regression model which will include fixed effects for treatment, region, and prior biologic exposure (yes/no). This will be evaluated using a linear contrast in which equal spacing between each of the doses is assumed. The coefficients for this linear contrast will be -2, -1, 0, 1, and 2 for placebo, bimekizumab 64mg Q4W, bimekizumab 160 Q4W, bimekizumab 320mg Q4W, and bimekizumab 480mg Q4W, respectively. While the bimekizumab 320mg loading dose followed by bimekizumab 160mg Q4W has been left out of the linear contrast for evaluating dose response, it will remain a part of the logistic regression model and will be compared to the bimekizumab 160mg Q4W dose. Prior biologic exposure was selected as a fixed effect in the logistic regression model as it is a stratification variable for randomization and because it may have an impact on efficacy. The use of region as a fixed effect in the model is also based on its use as a stratification variable in randomization and is intended to combine study centers into similar geographic regions. The geographic regions to be used will be defined in the IXRS and in the SAP. If the logistic regression model is unable to converge, then prior biologic exposure may be dropped from the model to facilitate convergence. The linear contrast from the logistic regression model will be evaluated at a 2-sided significance level of  $\alpha=0.05$ . This evaluation of dose-response will constitute the primary efficacy analysis.

As a supportive analysis for the primary efficacy variable, the same logistic regression model described above will be used to assess the effect of each individual dose vs placebo on PASI90 response. Comparisons will be made for each dose vs placebo at a 2-sided significance level of  $\alpha=0.05$ . For each dose, the odds ratio vs placebo, the 95% confidence interval, and the corresponding p-value will be calculated.

The pairwise comparisons of bimekizumab versus placebo will be formally evaluated for statistical significance only if the primary dose response efficacy analysis is statistically significant. Once the dose response has been established, pairwise testing of each bimekizumab dose versus placebo will account for multiplicity by using a fixed sequence testing procedure with each bimekizumab dose being tested sequentially from the highest dose to the lowest dose. Each test will only be conducted if the previous test reaches significance at a 2-sided significance level of  $\alpha=0.05$ . This procedure will control the overall Type I error rate. A pairwise comparison will also be made for the bimekizumab 160mg Q4W group versus the bimekizumab 320mg loading dose followed by bimekizumab 160mg Q4W group, but this evaluation will not be part of the sequential testing procedure described above (ie, the p-value will be nominal).

Non-responder imputation (NRI) will be used to account for missing data in the primary analysis. That is, subjects with a missing PASI score at Week 12 or who discontinued study treatment prior to the Week 12 Visit will be considered non-responders for the primary analysis.

#### **14.3.1.1 Sensitivity analyses**

The primary dose response analysis and pairwise comparisons will be repeated for all subjects in the PPS to evaluate the effect of important protocol deviations on the analysis.

An ordered categorical analysis using a non-parametric correlation statistic of Mantel and Haenszel (1959) and modified ridit scores will be performed as a sensitivity analysis to the primary dose-response evaluation based on the logistic regression model. This analysis will include region and prior biologic exposure as stratification factors to adjust for potential differences in the dose response based on these variables, and will be evaluated at a 2-sided significance level of  $\alpha=0.05$ .

Additional sensitivity analyses to evaluate the assumptions related to the handling of missing data for the primary efficacy variable will be performed and are described in greater detail in [Section 14.6](#).

#### **14.3.2 Other efficacy analyses**

##### **14.3.2.1 Analysis of the secondary efficacy variables**

The secondary efficacy variables will be analyzed for all subjects in the FAS.

All categorical variables (ie, PASI75/90/100 response, IGA response [clear, almost clear]) will be analyzed for treatment effects using pairwise comparisons based on the same method as that described for the primary efficacy variable.

Dose and exposure response will be assessed using a non-linear model assessing the relationship between dose/exposure and PASI score. The model will include fixed effects for dose/exposure and test the clinical and statistical relevance of covariate effects. Further details will be given in a separate data analysis plan (DAP) and reported in a separate document.

##### **14.3.2.2 Analysis of the other efficacy variables**

All other efficacy variables will be analyzed for all subjects in the FAS.

All categorical variables will be summarized using frequency tables by treatment group for each visit.

All continuous variables will be summarized using descriptive statistics by treatment group for each visit.

Time to PASI50, PASI75, PASI90, and PASI100 response will be estimated and presented using the Kaplan-Meier product-limit method for each treatment. Time to a given response will be defined as the length in days from Baseline until the first date when the response is achieved.

Subjects who discontinue study treatment prior to achieving a response will be censored at the date of study treatment discontinuation. Subjects who reach the Week 12 Visit without achieving the given response will be censored at the date of the Week 12 Visit. The median time to response, including the 2-sided 95% confidence interval, will be calculated for each treatment. Between group differences (each bimekizumab dose vs placebo) will be analyzed with the log-rank statistic.

All other efficacy variables will be summarized based on imputed data (NRI and last observation carried forward [LOCF] for binary and continuous variables, respectively) and observed case data (ie, subjects with missing data or who have prematurely discontinued study treatment are treated as missing).

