## 8 STUDY PROCEDURES BY VISIT

Table 5–1 (schedule of study assessments) provides a general overview of study assessments. A list of procedures to be completed at each visit is described below.

- Visit windows of +/-3 days on either side of the scheduled dosing are permitted; however, the Investigator should try to keep the subjects on the original dosing schedule. The window of +/-3 days is relative to Baseline and applicable for all subsequent visits. Changes to the dosing schedule outside of the 3-day window must be discussed with the Medical Monitor.
- The minimum of time between doses should be no less than 24 days and no more than 32 days.
- For the Safety Follow-Up Visit (20 weeks after the last dose), the visit should occur no more than 3 days prior to the scheduled visit date and within 7 days after the scheduled visit date (-3 days/+7 days)

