#### **14.8 Determination of sample size**

A total of 240 subjects (40 in each treatment group) are planned to be randomized in this study. The primary efficacy analysis will be based on the FAS. While some randomized subjects may not be in the FAS, it is expected that this number will not impact the following calculations.

The sample size is calculated based on published PASI90 response data from the secukinumab psoriasis program (ERASURE and FIXTURE studies) and from a Phase 2 bimekizumab study in subjects with psoriatic arthritis (PA0007). As an IL-17A inhibitor, the secukinumab data are important in the estimation of the response of bimekizumab, an IL-17A/F inhibitor. In the ERASURE and FIXTURE studies, PASI90 responses at Week 12 were reported to be 59.2% and 54.2% for the 300mg treatment group and 39.1% and 41.9% for the 150mg treatment group versus 1.2% and 1.5% in the placebo group, respectively (Langley et al, 2014). Limited data from a subset of subjects with psoriasis BSA >3% in the PA0007 study indicate a PASI90 response of 86.7% after 8 weeks of treatment for the combined top 3 doses versus no response in the placebo group.

For the sample size calculation, responder rates of 60%, 50%, and 2% at the end of a 12-week Treatment Period for bimekizumab 480mg Q4W, bimekizumab 320mg Q4W, and placebo have been assumed, respectively. These assumptions are similar to the results observed in the ERASURE and FIXTURE studies and conservative relative to the PA0007 study in order to

account for uncertainty in the estimates. The PASI90 responder rates for the 160mg Q4W, and 64mg Q4W doses are assumed to decrease, using estimates of 40% and 20%, respectively. Note that the bimekizumab 320mg loading dose followed by bimekizumab 160mg Q4W has been left out of this sample size calculation as it will not be included in the test for dose response, but will rather be compared separately to the bimekizumab 160mg Q4W dose.

The sample size for the primary objective of evaluating the dose response relationship was calculated using a 2-sided test for detecting a linear trend across proportions (Nam, 1987) at a significance level of 0.05. With 40 subjects in each treatment group, the test for detecting the overall dose response based on PASI90 response is powered at >99%.

The sample size calculations were performed using the software nQuery Advisor® 7.0.

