8.3.13 Analysis of SF-36

The change from Baseline in the SF-36 PCS and MCS scores as well as for the individual domain scores will be summarized at each visit by treatment group.

Confidential Page 36 of 63

As a sensitivity analysis the SF-36 PCS, MCS and individual domain scores will be also summarized at each visit and by treatment group for the complete cases, where any missing data or variations thereof will result in the affected domains and component scores for that visit also being set to missing.

8.3.14 **Definition of Time to PASI Response**

Time to PASI50, PASI75, PASI90, and PASI100 response (in days) will each be calculated as:

Date of first PASIx response – Date of Baseline visit +1

8.3.15 **Analysis of Time to PASI Response**

Time to PASI50, PASI75, PASI90, and PASI100 response will each be estimated and presented using the Kaplan-Meier product-limit method for each treatment group.

Kaplan-Meier plots of time to PASI50, PASI75, PASI90, and PASI100 response will be presented by treatment group.

Subjects who discontinue study treatment prior to achieving a response will be censored at the date of study treatment discontinuation. Subjects who reach the Week 12 Visit without achieving the given response will be censored at the date of the Week 12 Visit.

The median time to response, including the two-sided 95% confidence interval, will be calculated for each treatment. Comparisons of each bimekizumab dose vs placebo will be analyzed using a log-rank test stratified by region and prior biologic exposure. In addition between group differences for bimekizumab 320mg loading dose + 160mg O4W vs bimekizumab 160mg Q4W and bimekizumab 320mg loading dose + 160mg Q4W vs bimekizumab 320mg Q4W will be analyzed using the log-rank test stratified by region and prior biologic exposure.

Definition of Subject Symptom Diary responses 8.3.16

UCB is developing a new PRO measure that will be used to assess key symptoms relevant to subjects with moderate to severe chronic plaque psoriasis.

PS0010 will use the draft PRO measure in selected countries to enable psychometric validation of the PRO. Site staff will train the participating subjects on the use of the electronic PRO (ePRO) diary at the Screening visit, following which the device will be dispensed to the subject for home use until the Week 12 Visit.

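### Censoring Week 12 non-responders on their actual visit date inflates the tail of the time-to-PASI Kaplan-Meier curves after about Day 84 and can produce a median in an arm where fewer than half responded

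*Protocol*

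**What the plan says.** Protocol 14.3.2.2 measures time to response in days from Baseline to the first date on which the response is seen. For subjects who never respond it says: "Subjects who reach the Week 12 Visit without achieving the given response will be censored at the date of the Week 12 Visit". It adds: "The median time to response, including the 2-sided 95% confidence interval, will be calculated for each treatment".

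SAP 8.3.14 computes the event time from the actual response date and the Baseline date, plus one. SAP 8.3.15 repeats that subjects not achieving "the given response will be censored at the date of the Week 12 Visit", and plans curves and medians for all four PASI thresholds in every arm.

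The Week 12 date is not a single day. Protocol Section 8 says: "Visit windows of +/-3 days on either side of the scheduled dosing are permitted", and counts the window from Baseline for all later visits; Table 5–1 and the heading of 8.8 agree. SAP 3.9.2 also uses out-of-window measurements if they are in sequence. Neither document maps Week 12 to one analysis time, censors after the window closes, or uses an interval-censored estimator.

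**The concern.** PASI is read only at visits, and Week 12 is the last reading in the treatment period. A non-responder seen on Day 81 has finished follow-up and is known not to have responded. The rule nevertheless removes that subject on Day 81. A responder seen on Day 87 is then counted against the few subjects whose appointments fell late. Kaplan-Meier treats the Day 81 subject as someone who might still have responded over Days 82 to 87, although no later efficacy reading in the treatment period exists. The denominator therefore shrinks with appointment dates and not with response.

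Earlier visits do not have this problem, because non-responders stay at risk after them. Dropout is not needed, so this is separate from censoring at treatment discontinuation.

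At stake are the tail of each curve and the reported median. The planning rates in protocol 14.8 (40% for 160mg, 50% for 320mg) lie where a curve pushed upward can cross one half.

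**Working it through.** **The plan's own figure.** The documents give no figure for the time-to-response analysis. The only planned figure is the >99% power of the "2-sided test for detecting a linear trend across proportions (Nam, 1987) at a significance level of 0.05". With 40 per arm, scores −2 to 2 and rates 2/20/40/50/60%:

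- Expected statistic: 40 × (−0.04 − 0.20 + 0 + 0.50 + 1.20) = 58.4
- Null SD: √(0.344 × 0.656 × 40 × 10) = 9.50
- Alternative SD: √(40 × 1.4484) = 7.61
- z = (58.4 − 1.96 × 9.50)/7.61 = 5.23, so power exceeds 99.99%

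The stated power is reproduced and does not depend on the censoring rule. Only the arm size and planning rates are carried forward.

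**Worked arm.** An illustration, in days after Baseline (the SAP's plus one shifts every label by one). Of 40 subjects, 12 respond by Week 8. Of the other 28, four attend on each of Days 81 to 87, one responder among them each day. Ever responded: (12 + 7)/40 = 47.5%. Survival before Week 12 is 28/40 = 0.70 and is multiplied each day by (n − 1)/n.

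| Day | At risk | S | KM response |
|---|---|---|---|
| 81 | 28 | 0.675 | 32.5% |
| 82 | 24 | 0.647 | 35.3% |
| 83 | 20 | 0.615 | 38.5% |
| 84 | 16 | 0.576 | 42.4% |
| 85 | 12 | 0.528 | 47.2% |
| 86 | 8 | 0.462 | 53.8% |
| 87 | 4 | 0.347 | 65.3% |

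The curve ends at 65.3% against 47.5% observed, and a median appears on Day 86. On Day 84 it is still below 47.5%. The excess arises on the last two days, with 8 and then 4 subjects at risk.

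**General form.** Let S0 be the share not responding before Week 12, q the chance that such a subject first responds at Week 12, w_j the share attending on day j, and R_j the share still to attend at the start of day j. The curve ends at

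1 − S0 × Π(1 − q·w_j/R_j).

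Example: true rate 40%, 25% of responders first responding at Week 12, attendance uniform over seven days. S0 = 0.70, q = 0.10/0.70 = 1/7, and w_j/R_j = 1/7, 1/6, …, 1. After Day 84 the curve is at 37.3%; after Day 87 it is at 52.5%.

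**Simulation.** 40 per arm, no dropout. The documents give neither the attendance spread nor the share first responding at Week 12, so both are assumptions. The ranges below are mean end-of-curve values over four attendance patterns: 80% on Day 84, 50% on Day 84, triangular, and uniform.

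| True rate | 10% first at Week 12 | 25% | 40% |
|---|---|---|---|
| 20% | about 23% | 27–29% | 31–33% |
| 40% | 45–47% | 51–54% | 57–60% |
| 50% | 56–57% | 62–66% | 67–72% |
| 60% | 66–68% | 72–76% | 77–81% |

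A 2% placebo arm moves by at most about 2 points. Over a wider set of assumptions, the 40% arm ends on average at about 43% (90% of visits on Day 84, 10% first responding at Week 12) to 62% (wide spread, 50% first at Week 12). Among samples of that arm with under half responding, about 6% to 74% still report a median.

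The excess is skewed. With 70% on Day 84 and 25% first at Week 12, the mean for a 40% arm is about 53%, but the median excess per arm is about 3 points. If everyone attends on Day 84 the excess is exactly zero.

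**The case against.** Several points on the other side stand.

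- A reader might infer that the curves overstate response throughout, or at Week 12 as such. They do not. On average the curve at Day 84 is at or slightly below the proportion who ever respond by Week 12.
- A reader might infer that the distortion is always large. The documents do not support that, because both inputs that set its size are missing. Section 8 asks investigators to keep to the original dosing schedule, and 7.2 makes Week 12 a dosing visit for subjects entering the extension, so visits may cluster and the typical excess may be small.
- A median reached by Week 8 is unaffected. Protocol 14.8 cites an 86.7% PASI90 response after 8 weeks for the combined top three PA0007 doses, although the planning rates are much lower.
- A gap between these curves and the responder tables is not proof of this fault. The tables use non-responder imputation at a visit; the curves use first-ever response and censor treatment discontinuers.
- Time to PASI response is listed among the other efficacy variables and lies outside the fixed-sequence procedure. By-visit response summaries (SAP 8.3.2) show the actual rates.

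None of this repairs the rule. Clustered attendance reduces the average error but leaves a long upper tail, and nothing in either document prevents a false median.

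**Conclusion.** The concern holds in a limited form. As written, the rule gives a Kaplan-Meier tail that on average exceeds the proportion ever responding by Week 12, and it can give a median for an arm in which fewer than half responded. For a true 40% arm of 40 subjects the mean excess runs from about 3 to 22 points (43% − 40% to 62% − 40%), given no dropout and the assumed attendance spreads and late-response shares. It is zero with same-day attendance and confined to the days after about Day 84.

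A reader might go further and doubt the trial's main conclusions. The documents do not support that: the primary PASI90 analysis, its power and the secondary analyses do not use these dates, and the log-rank test remains valid under the null. The fault lies in the descriptive estimates, and it is worth correcting because the correction is cheap.

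**What to change.** In SAP 8.3.14 to 8.3.15, and in protocol 14.3.2.2, censor subjects who reach Week 12 without response at one common time no earlier than the last Week 12 event date. Without dropout the curve then ends exactly at the observed cumulative proportion, and no median can appear when fewer than half responded.

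Alternatively, run the analysis on nominal visit weeks (1, 2, 4, 6, 8, 12), so that Week 12 events and censorings share one time point. This version also needs a rule for treatment discontinuation between visits: assign discontinuers without response to the last nominal visit assessed before discontinuation.

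The cost is one SAP sentence and one derivation change, plus the discontinuation rule if nominal weeks are used. No new data are needed. The curves will look slightly less favourable.
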